6.9 Contraception and Pregnancy Avoidance Procedure

Subjects will be provided with information on acceptable methods of contraception as part of the subject informed consent process and will be asked to sign a consent form stating that they understand the requirements for avoidance of pregnancy, donation of ova, and sperm donation during the course of the study and for 90 days after the last dose of study drug. This may be signed by the LAR/caregiver of the subject. For additional details, refer to Section 6.6 for detailed contraception requirements.

Female subjects who have experienced menarche must have a negative serum/urine hCG pregnancy test at screening (Visit 1) and a negative serum hCG pregnancy test on Day 1 (Visit 2), before receiving any dose of study drug. If pregnancy results cannot be collected at Visit 2, the reason should be documented in the source document, the results of the serum pregnancy test obtained at Visit 1 must be confirmed to be negative by the Investigator prior to randomization, and results of a serum pregnancy test at Visit 2 must be confirmed to be negative before the subject can receive the first dose of study drug. During the study, subjects will receive continued guidance with respect to the avoidance of pregnancy and ova or sperm donation as part of the study procedures. An additional serum/urine hCG pregnancy test will be performed at the final visit.

7 Statistical and Analytical Plan

7.1 General Considerations

All statistical analyses will be performed using SAS[®] Version 9.4 or higher. All clinical study data will be presented in subject data listings. Data summaries will be presented for all endpoints and will include descriptive statistics (number of subjects, mean, SD, first quartile, median, third quartile, minimum, and maximum) for continuous variables, and frequency and percentage for categorical and ordinal variables. If there are missing values, the number of missing values will be presented, but without a percentage.

For all analyses, “baseline” refers to the most recent non-missing value obtained immediately prior to administration of first dose, unless it is otherwise clearly defined.

Any substantial change to the data analysis methods described in the protocol will require an amendment. Any other change to the data analysis methods described in the protocol, and the justification for making the change, will be described in the SAP. Additional post hoc analyses of the data may be conducted as deemed appropriate.

7.2 Endpoints

7.2.1 Efficacy Endpoints

7.2.1.1 Primary Endpoint

- The CGI-I-AS score at Week 12

[figure not shown]
[figure not shown]
7.2.1.2 Key Secondary Endpoints

[figure not shown]
The key secondary endpoints will be utilized to fulfil a recommendation of the EMA for a responder analysis.

- CGI-I-AS response (at least minimally improved) defined as CGI-I-AS score of 1, 2, or 3 at Week 12
- CGI-I-AS response (at least much improved) defined as CGI-I-AS score of 1 or 2 at Week 12

7.2.1.3 Other Secondary Endpoints

[figure not shown]
- 
- VABS-3 assessment scores; change from baseline to Week 12
 - Communication domain and its subdomains
 - Socialization domain and its subdomains
 - Daily Living Skills domain and its subdomains
 - Motor Skills domain and its subdomains
 - Maladaptive Behavior domain and its subdomains
 - The CGI-S-AS scores, change from baseline to Week 12.
 - The CGI-S-AS symptoms overall score
 - The CGI-S-AS domain scores
 - The relationship between CGI-S-AS at baseline and CGI-I-AS at Week 12
 - The relationship between each of CGI-S-AS domains at baseline and CGI-I-AS at Week 12
- 

[figure not shown]

7.2.2 Safety Endpoints

- Incidence of AEs
- Change in clinical laboratory parameters from baseline to each post baseline assessment
- Shift in clinical laboratory parameters from baseline to each post baseline assessment
- Change in vital sign measurements from baseline to each post baseline assessment
- Shift in physical examination parameters from baseline to each post baseline assessment
- Change in suicidality assessment (ABC-I) from baseline to each postbaseline as assessed by ABC-I. The ABC-I will serve as a surrogate measure for suicidality
- Percent change in seizure frequency (expressed as a 28-day frequency) from baseline to each post baseline timepoint

7.4 Analysis Sets

The following analysis sets will only include subjects 4 to 12 years old (inclusive). The analysis for subjects 2 to 3 years old (inclusive) will be conducted separately.

The intent-to-treat set will consist of all subjects who are randomized, whether or not study drug is received. Subjects will be analyzed according to their randomized group

The full analysis set (FAS) will include all subjects who are randomized, receive at least 1 dose of study drug, and have at least 1 post baseline assessment of the primary efficacy endpoint. The FAS will be used for efficacy analyses based on the randomized treatment for each subject.

The per protocol set (PPS) is a subset of the FAS that includes subjects who complete the Week 12 visit and have no major protocol deviations that are deemed to impact efficacy. The PPS will be used for efficacy analyses based on the randomized treatment for each subject.

The safety set (SS) will consist of all subjects who are randomized and receive at least 1 dose of study drug and will be used for all safety analyses. The safety analyses will be based on the treatment that was actually administered to each subject.

7.5 Subject Disposition

The number of subjects screened and who failed screening will be displayed. The number and percentage of subjects who are randomized, dosed, withdrawn from the study (including reasons for withdrawal), and complete the study will be displayed by treatment group and overall for the intent-to-treat set. The number and percentage of randomized subjects in the SS, FAS, PPS,   data set will also be displayed by treatment group and overall.

The number of subjects screened, dosed, completed study, and withdrawn from the study will be summarized separately for subjects 2 to 3 years old (inclusive).

7.6 Demographic and Baseline Characteristics

Demographic characteristics include age at screening and at baseline, age group (randomization stratification variable: age at screening 4 to 8 years versus age 9 to 12 years), region (randomization stratification variable: US versus outside US), gender, race, ethnicity, study center, and country. Baseline characteristics include baseline body weight, height, body mass index (kg/m^2), and molecular diagnosis. All demographic and baseline characteristics data will be summarized descriptively by treatment group and overall for the SS.

Data for subjects 2 to 3 years old (inclusive) will be presented separately in listings.

7.7 Exposure and Compliance

Treatment compliance will be summarized by treatment group over the entire treatment period. Compliance rates during the treatment period will be derived using the following formula:

$100 \times (\text{Total number of capsules dispensed} - \text{Total number of capsules returned}) / (\text{Expected number of capsules})$

The expected number of capsules to be taken is based on the date of first study drug dose and the date of last study drug dose, the subject's weight range band at screening that determines the number of capsules expected each study week, following the titration schedule (Section 5.1), and any dose down-titrations (Section 5.2.1). Compliance rates will be presented for the SS using summary statistics and percentage for the frequency distributions (0% to <20%, 20% to 40%, 40% to <60%, 60% to <80%, 80% to <100%, 100% to $\leq 120\%$) by treatment group and overall.

Data for subjects 2 to 3 years old (inclusive) will be presented separately in listings.

7.8 Efficacy Analyses

All efficacy analyses will be based on the FAS. Additionally, the analysis of the primary endpoint will be repeated on the PPS to assess the sensitivity of the results to major protocol violations. All efficacy variables will be summarized descriptively by treatment group and visit.

7.8.1 Primary Efficacy Analyses

The CGI-I-AS scale assessed by the clinician rater will be collected at the Week 6 and Week 12 visits. This is an ordinal variable with scores ranging from 1 (very much improved), to 4 (no change), to 7 (very much worse) which will be analyzed as a continuous outcome variable in these analyses.

An MMRM Analysis of Variance (ANOVA) model will be fitted using restricted maximum likelihood (REML) for CGI-I-AS with fixed effects for visit (Week 6 and Week 12), randomized treatment, the visit-by-treatment interaction, age group (randomization stratification variable: age 4 to 8 years versus age 9 to 12 years), and region (randomization stratification variable: US versus outside US). An unstructured within -subject covariance structure will be specified as the first choice, and if the model fails to converge, alternative covariance structures will be tested as detailed in the SAP. If a structured covariance is used, then a robust sandwich estimator will be utilized for estimating the variance of the treatment effect estimate. From the model, the Week 12 difference between least squared means of OV101 and placebo groups will be presented along with the corresponding 95% confidence interval and 2-sided *P* value.

[figure not shown]
As a sensitivity analysis for the assumption of normality, a Wilcoxon rank sum test will be used for treatment group comparison. The Hodges–Lehmann (Hodges and Lehmann 1963) estimate of

the median CGI-I-AS difference between OV101 and placebo groups, and its 95% confidence interval will be presented along with the 2-sided *P* value.

7.8.2 Key Secondary Efficacy Analyses

Generalized Estimating Equations (GEE) method will be used for the analysis of key secondary endpoints: CGI-I-AS response (at least minimally improved) and CGI-I-AS response (at least much improved). GEE models will include the response variable at each visit as the dependent variable, and fixed effects for visit (Week 6 and Week 12), randomized treatment, the visit-by-treatment interaction, age group (randomization stratification variable: age 4 to 8 years versus age 9 to 12 years), and region (randomization stratification variable: US versus outside US). An unstructured working correlation for the binary outcome variable will be assumed for the model parameter estimation, and if the model fails to converge, alternative covariance structures will be tested as detailed in the SAP. If there is no response in either treatment arm at the Week 6 visit, the GEE model will be substituted with a logistic regression for the Week 12 CGI-I-AS response variable with effects for the randomized treatment and the two randomization stratification variables. From the model (GEE or logistic regression, as appropriate), the Week 12 odds ratio will be presented along with the corresponding 95% confidence interval and 2-sided *P* value.

7.8.3 Other Secondary Analyses

[figure not shown]

The VABS-3 composite scores (Communications, Socialization, Daily Living Skills, Motor Skills, and Maladaptive Behavior domains) and scores of their subdomains will be assessed at baseline and Week 12 and analyzed as continuous outcome variables.

Change from baseline to Week 12 in each VABS-3 domain score and scores of their subdomains will be analyzed using an ANCOVA model with effects for randomized treatment, age group (randomization stratification variable: age 4 to 8 years versus age 9 to 12 years), region (randomization stratification variable: US versus outside US), and the corresponding baseline as a covariate. A test for a significant treatment-by-baseline interaction will be performed in a separate model (including the above terms plus the interaction term), using a 0.100 alpha level. If the treatment-by-baseline interaction is significant, then the ANCOVA assumptions are violated and an ANOVA model will be used instead. From the final model(s), the difference between least squared means of OV101 and placebo groups will be presented along with the corresponding 95% confidence intervals and 2-sided *P* values.

The CGI-S-AS Symptoms Overall and CGI-S-AS domains will be collected at baseline, Weeks 6, and 12, and will be treated as a continuous outcome variable. An MMRM ANCOVA methodology similar to the one described previously for [REDACTED] variables will be used to analyze the change from baseline in CGI-S-AS Symptoms Overall score and in scores of CGI-S-AS domains.

The relationships between CGI-S-AS Symptoms Overall score at baseline and CGI-I-AS at Week 12 will be explored. The relationships between each of CGI-S-AS domain scores at baseline and CGI-I-AS at Week 12 will also be explored.

7.8.5 Description of Subgroups to be Analyzed

Descriptive statistics will be presented separately by age group (randomization stratification variable: age 4 to 8 years versus age 9 to 12 years) for the primary endpoint and the two key secondary endpoints. Observed values will be reported by treatment group. The difference in means or proportions for OV101 versus placebo groups will also be presented with the corresponding 95% confidence intervals. Similar subgroup analysis will be conducted for region (US versus outside US).

If for a given endpoint, the results in the 2 subgroups appear different from a clinical perspective, the appropriate model (MMRM, GEE, or logistic) could be constructed as described above, including an age-by-treatment interaction term. This interaction term will be tested at alpha level of 0.10 to assess whether the treatment effects are statistically different for the 2 age subgroups.

7.9 Safety Analyses

All safety analyses will be based on the SS. Descriptive statistics will be used to summarize all safety endpoints by treatment group. Two-sided 95% CIs will be presented where meaningful. Data summaries will be displayed for incidence of AEs, clinical laboratory variables, vital signs, body weight and body mass index, physical examinations, clinical assessment of suicidality, and seizure diary data.

Unless otherwise specified below, safety data for subjects 2 to 3 years old (inclusive) will only be presented in listings and will be displayed in by-subject graphs, as appropriate.

7.9.1 Adverse Events

All TEAEs will be coded using MedDRA and will be summarized by MedDRA system organ class and preferred term and treatment group. Detailed listings of TEAEs, SAEs, related AEs, and discontinuations due to AEs will be provided.

The incidence of TEAEs, discontinuations due to TEAEs, drug-related, and serious TEAEs will be summarized. Incidence of TEAEs by severity and relationship to study drug will also be presented.

Incidence of TEAEs will be summarized separately for subjects 2 to 3 years old (inclusive).

7.9.2 Clinical Laboratory Tests

Changes from baseline to each post baseline visit with respect to clinical chemistry and hematology results will be summarized descriptively. Each laboratory parameter will be

classified as low, normal, or high relative to the parameter's reference range and will be summarized with shift tables. Listings of subjects with abnormal results will be provided.

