4.1.2 Exclusion Criteria

Subjects meeting any of the following criteria will be excluded from the study:

1. Has a circumstance or concomitant disease (e.g., gastrointestinal, renal, hepatic, endocrine, respiratory, or cardiovascular system disease), condition, or any clinically significant finding at screening that could interfere with the conduct of the study or that would pose an unacceptable risk to the subject in the opinion of the investigator.
2. Has poorly controlled seizures defined as any of the following:
 - a. Weekly seizures of any frequency with a duration more than 3 minutes.
 - b. Weekly seizures occurring more than 3 times per week, each with a duration of less than 3 minutes.
 - c. Investigator assessment.
3. Has any of the following laboratory abnormalities: total bilirubin $>1.5 \times$ upper limit of normal (ULN), unless known Gilbert's syndrome; alanine aminotransferase or aspartate aminotransferase $>2.5 \times$ ULN; serum creatinine $>1.2 \times$ ULN; absolute neutrophil count $<1.5 \times 10^9/L$; platelets $<80 \times 10^9/L$; hemoglobin <80 g/L; or thyroid-stimulating-hormone $>1.25 \times$ ULN or $<0.8 \times$ lower limit of normal. Retesting of clinical laboratory parameters may be allowed after consultation with the medical monitor or designee.

4. Use of benzodiazepines, zolpidem, zaleplon, zopiclone, eszopiclone, barbiturates, or ramelteon for sleep, or minocycline or levodopa within the 4 weeks prior to Day 1 or during the study. Benzodiazepines administered as needed for situational anxiety related to occasional procedures or events are permitted, and benzodiazepines are also permitted for seizure control.
5. 
6. Is at risk of harming self and/or others (based on investigator assessment).
7. Has enrolled in any interventional clinical study or used any investigational agent or device, or has participated in any investigational procedure, within the 30 days before screening or does so concurrently with this study.
8. Is allergic to OV101 or any excipients of study drug.
9. The subject or LAR/caregiver is unable to comply with study requirements (based on investigator assessment).
10. Is a family member of the investigator and/or study site staff.

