3.9.2 Clinical Laboratory Evaluation

A list of clinical laboratory tests is given below:

Hematology	
 - Hematocrit - Hemoglobin - Red blood cell count - Mean corpuscular volume - Mean corpuscular hemoglobin - Mean corpuscular hemoglobin concentration - Reticulocytes - White blood cell count 	
 - Neutrophils (% and count) - Lymphocytes (% and count) - Monocytes (% and count) - Eosinophils (% and count) - Basophils (% and count) - Platelet count - Prothrombin time - Partial thromboplastin time - International normalization ratio
Clinical Chemistry	
 - Albumin - Alkaline phosphatase - Blood urea nitrogen - Gamma-glutamyl transferase - Calcium - Creatinine - Glucose - Cholesterol, high-density lipoprotein [calculated] - Cholesterol, low-density lipoprotein [calculated] - Cholesterol, homogenous low-density lipoprotein - Triglycerides 	
 - Magnesium - Phosphate - Potassium - Alanine aminotransferase - Aspartate aminotransferase - Lactate dehydrogenase - Sodium - Chloride - Total bilirubin - Direct bilirubin - Total protein - Uric acid - Creatine phosphokinase
Pregnancy Testing¹	
 - Serum β-hCG or urine pregnancy testing for female subjects who have experienced menarche 	

¹ Pregnancy testing parameter will be listed only.

Continuous laboratory data will be examined for trends using descriptive statistics of observed values and changes from baseline to each planned post-baseline visit. These data will also be categorized as low, normal or high based on the reference ranges of the central/local laboratory. Frequencies and percentages will be presented for the shifts in these categories from baseline to each post-baseline visit (i.e., low to normal, low to high, high to low, etc.) for all applicable laboratory parameters listed above. The analyses will be performed using the SS and presented by treatment group.

A separate listing for all clinically significant laboratory abnormalities will be provided.

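### Laboratory shift tables use only low/normal/high although children may enter out of range, so no planned table counts by arm how many go beyond a numeric limit

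*Protocol*

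**What the plan says.** Laboratory shift from baseline is a named safety endpoint (Protocol 7.2.2, SAP 3.3.6). Protocol 7.9.2 gives it three levels: each parameter is "classified as low, normal, or high relative to" its reference range, and the result goes into shift tables. SAP 3.9.2 keeps the three levels: "These data will also be categorized as low, normal or high based on the reference ranges of the central/local laboratory".

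Both documents also plan descriptive statistics of the laboratory results. Under SAP 3.1.2 these are n, mean, SD, quartiles, minimum and maximum by treatment group, and SAP 3.9.2 applies them to observed values and to changes. SAP 3.1.2 puts all study data in subject listings, and SAP 3.9.2 adds: "A separate listing for all clinically significant laboratory abnormalities will be provided".

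Entry does not require normal values. Exclusion criterion 3 (Protocol 4.1.2) removes a child only for:
- "total bilirubin $>1.5 \times$ upper limit of normal (ULN), unless known Gilbert's syndrome"
- "alanine aminotransferase or aspartate aminotransferase $>2.5 \times$ ULN"
- "serum creatinine $>1.2 \times$ ULN"
- neutrophils below 1.5 × 10⁹/L, platelets below 80 × 10⁹/L, haemoglobin below 80 g/L, or a TSH outside stated bounds.

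Neither document plans grading, a multiple-of-ULN category, or a by-arm count of children beyond any numeric limit.

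**The concern.** A three-level shift table suits a trial in which everyone starts within range. Here a child may start above the upper limit, or below the lower limit where the laboratory's range allows it. Such a child has no worse category to move to. Deterioration then appears as *high to high* or *low to low*, in the same cell as a child who has not changed. For a child normal at baseline the shift does register, but its size is lost.

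At stake is the comparison between arms of a hepatic, renal or haematological change confined to a few children. With about 45 per arm, a count of children beyond a stated level is the natural display for such a change, and the plan has none.

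**Working it through.** The documents state no rate or figure for this point, so there is nothing to reproduce. The check applies the planned rule to example values.

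**Inputs**
- Three categories: Protocol 7.9.2, SAP 3.9.2.
- Entry limits: Protocol 4.1.2, criterion 3.
- About 45 children per arm, ages 4 to 12: SAP 2.2.1.
- Individual values and event rates below are assumptions for illustration.

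**1. What the shift table shows** (multiples of ULN)

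| Analyte | Baseline | Post-baseline | Cell | Beyond entry limit? |
|---|---|---|---|---|
| ALT/AST | 2.0 | 2.4 | high to high | no |
| ALT/AST | 2.0 | 2.6, 5 or 10 | high to high | yes |
| Bilirubin | 1.4 | 1.6 or 3 | high to high | yes |
| Creatinine | 1.1 | 1.3 or 2 | high to high | yes |
| ALT/AST | 0.9 | 1.1 | normal to high | no |
| ALT/AST | 0.9 | 10 | normal to high | yes |

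The cell does not tell the last column apart, whether baseline is high or normal.

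**2. What the mean shows.** If k of 45 children each rise by d, the arm mean moves by k × d / 45.
- k = 1, d = 4 × ULN: 4/45 = 0.09 × ULN.
- d = 8 × ULN: 8/45 = 0.18 for one child, 16/45 = 0.36 for two, 24/45 = 0.53 for three.

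**3. How much depends on baseline.** Suppose 3 of 45 children on OV101 and 0 of 45 on placebo go newly beyond a limit. If j of the three were normal at baseline and the rest already out of range in the same direction, the shift table shows j versus 0 category changes, with j anywhere from 0 to 3. A count of children newly beyond the limit shows 3 versus 0 in every case.

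**4. Whether a count would have content.** If the true rate of passing a limit is p, the chance of at least one such child among 45 is 1 − (1 − p)^45. This is 0.60 at p = 2%, 0.90 at 5% and 0.99 at 10%.

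**5. Whether the other displays supply the count**
- Minimum and maximum by arm show an extreme, not how many children reached it.
- The protocol synopsis allows safety laboratory tests at unscheduled visits. SAP 3.1.8 maps unscheduled results to windows and selects the nominal-visit record where one exists. The Week 6 window is Days 22 to 64, so a peak on an unscheduled Day 50 visit is passed over if the Week 6 visit value is present. It then enters neither the by-visit statistics nor the shift table.
- A laboratory finding reaches the AE tables only when the investigator considers it clinically significant (Protocol 6.4.1.4). No numeric limit applies.
- Listings hold the values but do not compare arms.

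**The case against.** The protocol and SAP agree on three levels, and all laboratory analysis is descriptive, so nothing is contradictory. The maximum change by arm would usually expose a child going from 1.1 to 5 × ULN. Protocol 6.4.1.4 makes clinically significant worsening from baseline an AE, and AEs are tabulated by arm. The IDMC reviews aggregate and individual safety data (Protocol 11.1.1). Exclusion 1 also removes children with clinically significant screening findings that could interfere with the study or pose unacceptable risk, so fewer may enter out of range than criterion 3 alone allows. Finally, the table could be built later from the full data.

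Most of this stands as partial cover. None of it yields a planned by-arm count, and a table specified before unblinding is more convincing than one built afterwards.

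Three stronger readings are tempting, and the documents do not support them.
- A reader might infer that the SAP narrows the protocol's listing of abnormal results to clinically significant ones, so that data are lost. SAP 3.1.2 lists all data, and the SAP 3.9.2 listing is described as separate, that is, additional.
- A reader might infer that a signal in a few children would show in neither the shift table nor the mean change. The shift table fails completely only for children already out of range at baseline; for a child normal at baseline the shift still appears and only its size is lost.
- A reader might treat the criterion 3 values as on-treatment safety limits. They are entry limits. Protocol 4.2.1 allows withdrawal when a child no longer meets the entry criteria, but its laboratory reason is qualitative and no numeric on-treatment limit is set.

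Local laboratories add some difficulty in reading a maximum as a multiple of ULN. However, central analysis is the default (Protocol 6.8), and the documents do not state the units of the summaries, so little weight rests on this.

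**Conclusion.** The point holds as a gap in the safety display. For children already out of range at baseline, the shift table cannot show further worsening in the same direction. For children normal at baseline, it cannot separate a trivial move from a large one. No planned table counts by arm the children beyond a numeric limit.

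The practical size cannot be fixed from the documents, because they do not say how many children enter out of range. In the assumed 3 versus 0 example, the shift table shows anything from 0 versus 0 to 3 versus 0. For neutrophils, platelets and haemoglobin the entry limits are absolute values, so the width of the low-but-admitted band depends on laboratory ranges that the documents do not give.

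The gap touches no efficacy conclusion and loses no data. It is worth closing because the remedy is cheap and uses cut-offs already in the protocol.

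**What to change.** In SAP 3.9.2, for total bilirubin, ALT, AST, creatinine, neutrophils, platelets and haemoglobin:

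1. Split the out-of-range category in the relevant direction at the criterion 3 entry limit (within, beyond). For limits expressed against ULN, use the ULN of the laboratory that ran the sample.
2. Tabulate by arm, in the safety set aged 4 to 12, the n (%) of children newly beyond the limit. This means not beyond it at baseline and beyond it at any post-baseline assessment, including unscheduled visits.
3. For bilirubin, show children with known Gilbert's syndrome separately, since criterion 3 exempts them.
4. State that these are entry limits used as descriptive cut-offs only and that they set no management rule.

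All seven analytes are in the laboratory lists of Protocol 6.7 and SAP 3.9.2. TSH is in criterion 3 but on neither list, so it is left out. The SAP already classifies by central or local reference range, so the ranges are needed in any case.

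The cost is a few lines of SAP text and one table, with no new data, visits or blood. The downside is one more descriptive table with small counts, which should be read without formal testing.
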